3.5 Secondary Study Endpoints

Pharmacodynamics and Cellular Immune Responses to Influenza Vaccination

- Time to onset and the number of upper-respiratory infections, including (but not limited to) influenza viral infections (as indicated by subject self-reporting)
- Changes in the concentration of circulating plasma cytokines including (but not limited to): IL-6 and G-CSF as pharmacodynamic indicators of entolimod's activity (measured using MSD assay platform)
- Changes to 10 cytokine/chemokine mediators of adaptive immune function (IFN- γ , IL-1 β , IL-2, IL-4, IL-6, IL-8, IL-10, IL-12p70, IL-13 and TNF- α) in PBMC culture supernatants at 0 and 24 hours after influenza (A/H1N1, A/H3N2 and B) viral stimulation as detected by Meso Scale Discovery, V-PLEX Proinflammatory panel human immunoassay kits.
- Changes in the quantification of IFN γ -positive cells as a marker of cell-mediated immunity (CMI) after vaccination using influenza virus-specific IFN- γ ELISPOT assay kits from R&D Systems.

- Changes in frailty indices and quality of life (QoL) of individuals receiving entolimod versus placebo
- Changes in measures of physical function (6-minute walk test, grip strength) and body composition

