[b] Physical examination will be limited to cardiac, pulmonary, abdominal, integumentary, and gross neurological evaluation, and to other systems based on specific subject complaints.
[c] Height will only be collected at screening; weight will be collected at all in-person visits
[d] To be collected pre-treatment and 2, 4 and 6 hours post treatment. Wt will only be performed prior to study drug administration.
[e] Serum chemistry studies will include sodium, potassium, chloride, bicarbonate, BUN, creatinine, glucose, calcium, phosphorus, magnesium, total protein, albumin, ALT, AST, ALP, CK, LDH, GGT, total bilirubin, uric acid, and CRP.
[f] Hematology parameters will include hematocrit, hemoglobin, erythrocyte count; absolute counts of leukocytes, neutrophils, lymphocytes, monocytes, eosinophils, basophils; platelet count.
[g] Coagulation studies will include PT and aPTT.
[h] Virology evaluation includes serum CMV, HIV antibody, HBsAg antibody, HBC antibody, HCV antibody. Subjects with a positive antibody evaluation for HBC or HCV should undergo evaluation for HBV DNA and for HCV RNA to determine if the antibody test may be falsely positive. Only CMV testing will be carried out on months 1 and 2.
[i] Urinalysis will include specific gravity, pH, protein, glucose, ketones, bilirubin, urobilinogen, blood, nitrite, leukocyte esterase as assessed by dipstick and microscopic urinalysis evaluating white blood cells, red blood cells, epithelial cells, bacteria, casts, and crystals.
[j] Test will be performed by GPI. Samples may also be used for additional testing related to the study objectives.
[k] G-CSF and IL-6 tests will be performed using the MSD assay platform. Samples are to be collected pre-treatment and 2, 4 and 6 hours post treatment.
[l] Influenza antibody titers A/H1N1, A/H3N2, and B assessed by HAI Assay
[m] Meso Scale Discovery, V-PLEX Proinflammatory panel for 10 cytokine/chemokine mediators of adaptive immune function (IFN- γ , IL-1 β , IL-2, IL-4, IL-6, IL-8, IL-10, IL-12p70, IL-13 and TNF- α) and Interferon gamma ELISPOT assay
[n] Sub-hertz Analysis of ViscoElasticity (SAVE) will be performed 6 hours after study drug administration (or placebo) on left and right deltoid muscles in cohorts receiving entolimod (3 μ g and 10 μ g) and representing a total of 50 subjects.
[o] Blood and urine will be collected for analyses of senescence
[p] Subjects will be contacted bi-weekly via the telephone for remote follow-up visits

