The distribution of antibody titers (A/H1N1, A/H3N2, B) during follow up is anticipated to be skewed based on reporting in prior studies and a log-transformation will be applied to these outcomes. Antibody titers are measured at multiple time points in the first week after treatment, 4 weeks, 2 months, 6 months, and 12 months. A hierarchical mixed-effects regression model will be fit separately for the 3 endpoints, adjusting for the baseline/screening observation of the titer (an analysis of covariance (ANCOVA) approach). The model will include random subject-specific intercepts and model time as discrete. The primary outcome comparison is a contrast analysis of the outcome at 4 weeks comparing each entolimod dose to placebo. As the overall aim of this study is to assess safety and identify potential efficacy of entolimod, especially the dose most likely to succeed in Phase III study, we apply a one-sided test at alpha level 0.15 to each dose comparison (vs. placebo) and antibody titer combination, without multiplicity adjustment. The primary analysis will be conducted using the modified intent-to-treat analysis dataset.

Secondary Hypotheses: Secondary and exploratory endpoints require a variety of standard statistical methods.

Key secondary endpoints include the frailty indices, measures of physical function (6 minute walk test and grip strength), and quality of life (QOL). Frailty indices are measured at 2, 6, and 12 months and QOL measured at each study visit. For these outcomes, linear mixed effects models will assess the relationship between randomized arm and outcomes over time. Discrete times will be considered corresponding to the study visit and secondary analyses may consider continuous linear time (constant slope over time) for changes in the outcome. For these outcomes, the 12 month observation is the primary comparison.

Upper respiratory infections, including influenza, will be recorded over the follow up period. We anticipate the total number of these will be infrequent. Thus, we compare the outcome of any infection (vs. no infection) across randomized arms using a Pearson chi-square test or Fisher's exact test. Secondary approaches may consider analysis of the ordinal count of the number of infections, analyzed using a trend test.

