Cellular immune response and pharmacodynamics parameters, including concentration of circulating plasma cytokines and cytokine response to viral stimulation are outcomes compared using analysis of variance (ANOVA) methods across the four comparison groups. Pharmacodynamic measures will be listed and will be summarized using appropriate graphical and tabular methods. Statistical analysis evaluating pharmacodynamic parameters will be performed using contrasts in the context of analysis of covariance (ANCOVA).

Handling of Missing Data

In the analysis of primary outcomes, data are analyzed using a hierarchical regression approach assuming missing data are missing at random. In a secondary approach, patients with dropout or missing follow up due to influenza viral infection during follow up will be assumed missing not at random and missing data will be imputed to the baseline/screening value reflecting no increase

from baseline in antibody titers among these patients. Dropout for other causes will be considered similarly, except death unrelated to influenza, which will continue to be assumed as missing at random.

Interim Analysis

No interim analysis will be performed for efficacy assessment.

Multiplicity

No adjustments will be made for multiplicity correction to dose comparisons or the primary endpoints as the study aim is to identify promising doses for subsequent phase III study. Secondary outcomes will also not be adjusted for multiple comparisons.

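### Section 7.2 gives the pharmacodynamic outcomes two unreconciled analyses and the cellular immune outcomes only an under-specified ANOVA, with no stated baseline covariate, scale or handling of repeated samples

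*Combined protocol and SAP*

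**What the plan says.** Section 7.2 opens the relevant paragraph with "Cellular immune response and pharmacodynamics parameters, including concentration of circulating plasma cytokines and cytokine response to viral stimulation" and says that these are "outcomes compared using analysis of variance (ANOVA) methods across the four comparison groups". After a sentence on listings and graphs it adds: "Statistical analysis evaluating pharmacodynamic parameters will be performed using contrasts in the context of analysis of covariance (ANCOVA". The ANCOVA sentence names pharmacodynamic parameters only; cellular immune response appears only under ANOVA.

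The paragraph gives no covariate, scale, time point, contrast set or test level. For the antibody titers, the same section states that "a log-transformation will be applied to these outcomes", adjusts for the baseline titer, models time as discrete with random subject intercepts, and names the contrast of each dose with placebo at 4 weeks.

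Section 3.5 defines the endpoints as changes: "Changes in the concentration of circulating plasma cytokines including (but not limited to): IL-6 and G-CSF" and, for ELISPOT, "Changes in the quantification of IFN γ -positive cells". On plasma sampling, footnote [k] to Table S-1 reads: "Samples are to be collected pre-treatment and 2, 4 and 6 hours post treatment". The PBMC row of that table covers the treatment visit and Months 1, 2 and 12, and Section 6.2 lists a PBMC draw before vaccine and study drug.

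**The concern.** A four-group ANOVA asks whether any arm differs. Contrasts within ANCOVA ask how each dose compares with placebo, given the pre-dose level. These are different questions, and for plasma IL-6 and G-CSF the plan names both without saying which is reported as the result. Secondary outcomes carry no multiplicity adjustment, so nothing else restrains a choice between the two after the data are seen.

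For the cellular outcomes the difficulty is efficiency. A pre-dose sample exists, yet the only named method does not say that it is used. Plasma is sampled three times after dosing and PBMC at three later visits, but no time point, summary measure or repeated-measures structure is given.

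Section 3.5 treats IL-6 and G-CSF as indicators of entolimod's activity, so an inefficient or ambiguous analysis weakens the evidence that the drug is active at these low doses.

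**Working it through.** The plan gives no power figure for these outcomes, so there is none to reproduce. The check compares the candidate analyses under common inputs.

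**Inputs**
- From the plan: 25 per arm, four arms (Section 7.1).
- Assumed: true fold changes 1, 1.2, 1.5, 2; correlation between log pre-dose and log post-dose values ρ = 0.6; 5% F-test.
- Log SD σ: 1.0 (assumed), and 1.27, which is √ln(1 + 2.0²) = √1.609. The CV of 2.0 is the plan's assumption for A/H1N1 titers, borrowed here. The plan gives no CV for any cytokine.

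**Power on the log scale**

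The noncentrality is λ = n·Σ(μᵢ − μ̄)² / (σ²·k). The factor k is 1 for an ANOVA of post-dose values, 2(1 − ρ) = 0.80 for an ANOVA of changes, and 1 − ρ² = 0.64 for ANCOVA. The F-test has 3 and 96 degrees of freedom (95 for ANCOVA).

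The log means are 0, 0.182, 0.405 and 0.693, with mean 0.320. The squared deviations sum to 0.268, and 25 × 0.268 = 6.70.

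| Analysis | λ, σ = 1.0 | Power | λ, σ = 1.27 | Power |
|---|---|---|---|---|
| ANOVA, post-dose | 6.70 | 55% | 4.16 | 36% |
| ANOVA, change | 8.37 | 66% | 5.20 | 44% |
| ANCOVA | 10.46 | 76% | 6.50 | 54% |

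Simulation of the same scenario gives 53%, 66% and 76%, and 36%, 43% and 53%, within about 2 points.

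**What an untransformed analysis would add**

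Simulated ANOVA of untransformed post-dose values has 34 to 37% power at σ = 1.0 and 17% at σ = 1.27. Against 76% and 53% that is a loss of more than half. An ANOVA of untransformed changes has 43% and 21%.

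**Effect of the baseline alone, as ρ varies**

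Here the scale is the same, the contrast is top dose against placebo, the test is two-sided at 5%, and the effect is set so that ANCOVA has 80% power.

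| ρ | 0.3 | 0.5 | 0.7 | 0.8 | 0.9 |
|---|---|---|---|---|---|
| ANOVA, post-dose | 76% | 68% | 52% | 39% | 23% |
| ANOVA, change | 62% | 68% | 73% | 76% | 78% |

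A loss of more than half from the baseline alone therefore needs ρ of about 0.8. At the one-sided 0.15 level used for the titers, the post-dose row is 78%, 72%, 62%, 54% and 41%, so half is never lost in this range. If an overall F-test with a linear dose pattern replaces the contrast at two-sided 5%, post-dose power is 39% at ρ = 0.7.

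**Large effects**

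With a 5-fold rise at the top dose and CV 2.0, every log-scale analysis has 96% power or more, and the untransformed ANOVA has 71 to 73%. At 10-fold the untransformed ANOVA has 91 to 92%.

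**The case against.** The strongest reply is that the paragraph is terse rather than wrong. The ANOVA can be read as the overall four-group comparison and the ANCOVA contrasts as its follow-up for pharmacodynamics. On that reading the preferred type of analysis is already named for IL-6 and G-CSF. The wording about ANOVA methods is generic and does not exclude repeated measures. This is a fair reading, but the plan does not state it, and it leaves the cellular outcomes with the ANOVA alone.

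A reader might also infer stronger points that the documents do not support:

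- **That the ANOVA is on the raw scale.** Section 7.2 is silent on scale here. Tying the log transform to titers does not prescribe untransformed analysis elsewhere.
- **That the pre-dose sample is discarded.** Section 3.5 defines the endpoints as changes, and an ANOVA of changes uses that sample. What can be said is that its use in the model is not stated. For stimulated cytokines, the 0 and 24 hours in Section 3.5 are culture times, so that change need not be from pre-dose.
- **That cellular outcomes are also assigned to both methods.** They are named only in the ANOVA sentence.
- **That over half the power is lost.** In the scenario above this needs an untransformed analysis; on a common scale with the same contrast it needs ρ near 0.8 or higher.
- **That dose choice would be misled.** The plan's dose inference rests on the 4-week titers, and cytokines are not among its key secondary endpoints.

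Section 1.4.2.1 reports substantial dose-related rises in G-CSF and IL-6, though mostly at higher doses than those planned here. If effects at 1 to 10 µg are also large, the choice of model matters little for plasma cytokines. That argument does not extend to the cellular outcomes.

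**Conclusion.** The point holds as a minor one. Two analyses are named for the pharmacodynamic outcomes and not reconciled. The cellular outcomes have one analysis, which states no baseline covariate, scale or handling of repeated samples, although the trial collects the data for a better one.

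In the assumed scenario, moving from a log-scale ANOVA to a log-scale ANCOVA gains about 10 points if the ANOVA is on changes, and 17 to 23 points if it is on post-dose values. The size depends on the assumed correlation, spread and fold changes, none of which the documents give for these outcomes, and it shrinks towards nothing when effects are large. The outcomes are secondary and unadjusted, and the primary titer analysis is unaffected.

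**What to change.** Replace the ANOVA sentence, for both pharmacodynamic and cellular outcomes, with one model that follows the titer model in Section 7.2:

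- log-transformed values as outcome, with a stated rule for zero counts and values below the assay limit;
- the log pre-dose value as covariate;
- discrete time by arm with random subject intercepts: 2, 4 and 6 hours for plasma, visit for PBMC;
- contrasts of each dose with placebo at a named time point, with the test level given.

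Deleting the ANOVA sentence without extending the ANCOVA sentence would leave the cellular outcomes with no method. An overall four-group test, if wanted, can come from the same model. A dose trend and sex as a covariate are optional.

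Two definitions should be settled in the same edit. One is whether the stimulated-cytokine value is the 24-hour level or its ratio to 0 hours. The other is whether cytokines listed in the blood work of Sections 6.3 and 6.5 to 6.8 belong to this analysis, since the plasma pharmacodynamics row of Table S-1 shows the treatment visit only.

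The cost is SAP wording, best settled before unblinding, and reporting results as geometric mean ratios. No extra sample or visit is needed.

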7.3 Subject Population(s) for Analysis

The primary analysis uses a modified intent-to-treat principle. Patients will be analyzed based on randomized arm using methods described previously. Exploratory analyses will assess whether a differential sex-based response to treatment exists for the primary outcomes and secondary outcomes of FI and QOL, using interaction terms in regression models.

8 Safety and Adverse Events

For safety analyses, AEs will be classified using the Medical Dictionary for Regulatory Activities (MedDRA). The severity of AEs will be graded by the investigator according to the Guidance for Industry Toxicity Grading Scale for Healthy Adult and Adolescent Volunteers Enrolled in Preventive Vaccine Clinical Trials. Concomitant medication use will be coded using the World Health Organization Drug Dictionary (WHODRUG) into Anatomical Therapeutic-Chemical classification (ATC) codes; these data descriptions will particularly focus on supportive medications and care provided in response to any study-study-induced adverse effects and to therapies for GVHD. For ECG assessment of QT intervals, correction by both the Bazett and Fridericia methods will be applied, and the data will be summarized by CTCAE grading categories in terms of absolute QTc and maximal QTc change from baseline.

A safety analysis will be conducted after 20 patients (5 per arm) have been randomized and completed the one-week safety follow-up period. After the last subject has completed their one-week safety follow-up period, there will be a temporary halt in additional participation pending analysis of safety outcomes, anticipated to be no longer than seven days. A safety report will be generated after the 20th patient completes 1 week follow up, summarizing all adverse events overall and by study arm while maintaining blind (groups denoted as A-D in random order). If appropriate, as described below, unblinded and subject-level adverse event data will be provided. Adverse events, both short term (14 days) and long term (through 365 days), will continue to be collected with ongoing monitoring as specified in the Data Safety Monitoring Plan (DSMP).

8.1 Definitions

Unanticipated Problems Involving Risk to Subjects or Others (UPIRTSO)

Any unanticipated problem or adverse event that meets the following three criteria:

- **Serious**: Serious problems or events that results in significant harm, (which may be physical, psychological, financial, social, economic, or legal) or increased risk for the subject or others (including individuals who are not research subjects). These include: (1)

death; (2) life threatening adverse experience; (3) hospitalization - inpatient, new, or prolonged; (4) disability/incapacity - persistent or significant; (5) birth defect/anomaly; (6) breach of confidentiality and (7) other problems, events, or new information (i.e. publications, DSMB reports, interim findings, product labeling change) that in the opinion of the local investigator may adversely affect the rights, safety, or welfare of the subjects or others, or substantially compromise the research data, **AND**

- Unanticipated: (i.e. unexpected) problems or events are those that are not already described as potential risks in the protocol, consent document, not listed in the Investigator's Brochure, or not part of an underlying disease. A problem or event is "unanticipated" when it was unforeseeable at the time of its occurrence. A problem or event is "unanticipated" when it occurs at an increased frequency or at an increased severity than expected, **AND**
- Related: A problem or event is "related" if it is possibly related to the research procedures.

Adverse Event

An untoward or undesirable experience associated with the use of a medical product (i.e. drug, device, biologic) in a patient or research subject.

Serious Adverse Event

Adverse events are classified as serious or non-serious. Serious problems/events can be well defined and include;

- death
- life threatening adverse experience
- hospitalization
- inpatient, new, or prolonged; disability/incapacity
- persistent or significant disability or incapacity
- birth defect/anomaly

and/or per protocol may be problems/events that in the opinion of the sponsor-investigator may have adversely affected the rights, safety, or welfare of the subjects or others, or substantially compromised the research data.

All adverse events that do not meet any of the criteria for serious, should be regarded as **non-serious adverse events**.

Adverse Event Reporting Period

For this study, the study treatment follow-up period is defined as (365) days following the last administration of study treatment.

Preexisting Condition

A preexisting condition is one that is present at the start of the study. A preexisting condition should be recorded as an adverse event if the frequency, intensity, or the character of the condition worsens during the study period.

General Physical Examination Findings

At screening, any clinically significant abnormality should be recorded as a preexisting condition. At the end of the study, any new clinically significant findings/abnormalities that meet the definition of an adverse event must also be recorded and documented as an adverse event.

Post-study Adverse Event

All unresolved adverse events should be followed by the sponsor-investigator until the events are resolved, the subject is lost to follow-up, or the adverse event is otherwise explained. At the last scheduled visit, the sponsor-investigator should instruct each subject to report, to the sponsor-investigator, any subsequent event(s) that the subject, or the subject's personal physician, believes might reasonably be related to participation in this study.

Abnormal Laboratory Values

A clinical laboratory abnormality should be documented as an adverse event if it changes from value within the normal range before treatment to one outside and worse than the normal range after treatment. Such changes will prompt a repeat test, telephone call to check the subject's status, a repeat visit, and/or referral to the subject's primary care physician.

Hospitalization, Prolonged Hospitalization or Surgery

Any adverse event that results in hospitalization or prolonged hospitalization should be documented and reported as a serious adverse event unless specifically instructed otherwise in this protocol. Any condition responsible for surgery should be documented as an adverse event if the condition meets the criteria for an adverse event.

Neither the condition, hospitalization, prolonged hospitalization, nor surgery are reported as an adverse event in the following circumstances:

- Hospitalization or prolonged hospitalization for diagnostic or elective surgical procedures for a preexisting condition. Surgery will **not** be reported as an outcome of an adverse event if the purpose of the surgery was elective or diagnostic and the outcome was uneventful.
- Hospitalization or prolonged hospitalization for therapy of the target disease of the study, unless it is a worsening or increase in frequency of hospital admissions as judged by the clinical investigator.
- A visit to the emergency department or other hospital department <24 hours, that does not result in admission (unless considered an important medical or life-threatening event).
- Elective surgery planned prior to signing consent.
- Admissions as per protocol for a planned medical/surgical procedure.
- Routine health assessment requiring admission for baseline/trending of health status (e.g., routine mammogram).
- Medical or surgical admission other than to remedy ill health and planned prior to entry into the study. Appropriate documentation will be obtained in these cases.

Recording of Adverse Events

At each contact with the subject, the study team must seek information on adverse events by specific questioning and, as appropriate, by examination. Information on all adverse events should be recorded immediately in the source document, and also in the appropriate adverse event section of the case report form (CRF) or in a separate adverse event worksheet. All clearly related signs, symptoms, and abnormal diagnostic, laboratory or procedure results should be recorded in the source document.

All adverse events occurring during the study period must be recorded. The clinical course of each event should be followed until resolution, stabilization, or until it has been ultimately determined that the study treatment or participation is not the probable cause. Serious adverse events that are still ongoing at the end of the study period must be followed up, to determine the final outcome. Any serious adverse event that occurs during the Adverse Event Reporting Period and is considered to be at least possibly related to the study treatment or study participation should be recorded and reported immediately.

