3.4 Primary Study Endpoints

Immunogenicity

- Changes of the anti- A/H1N1, anti-A/H3N2, and anti-B influenza virus strains serum circulating antibodies (as assessed using hemagglutination inhibition (HAI) assay) levels.

Safety

- All adverse events (AEs), including dose limiting toxicities (DLTs); laboratory abnormalities; oxygen saturation and vital sign changes, and adverse electrocardiogram (ECG) findings

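### Section 8.1 exempts the underlying condition, not only the hospital contact, from adverse event reporting in two circumstances that can cover new illness, which contradicts an all-AE primary safety endpoint

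*Combined protocol and SAP*

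**What the plan says.** Under the heading on hospitalization and surgery in section 8.1, the default is that an AE leading to hospitalization is a serious adverse event (SAE) unless the protocol instructs otherwise. The instruction follows directly: "Neither the condition, hospitalization, prolonged hospitalization, nor surgery are reported as an adverse event in the following circumstances". Most listed circumstances are elective, planned or routine care. Two are not confined to such care:

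- "A visit to the emergency department or other hospital department <24 hours, that does not result in admission", with an exception for events considered important medical or life-threatening.
- "Hospitalization or prolonged hospitalization for therapy of the target disease of the study, unless it is a worsening or increase in frequency of hospital admissions", the exception being left to the clinical investigator's judgement.

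The next heading in section 8.1 says, without qualification: "All adverse events occurring during the study period must be recorded". Section 3.4 lists among the primary endpoints, under safety: "All adverse events (AEs), including dose limiting toxicities (DLTs); laboratory abnormalities; oxygen saturation and vital sign changes". Section 8.1 also makes worsening of a preexisting condition an AE. The study title describes the subjects as healthy, and no section names a target disease.

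**The concern.** A list of this kind normally settles whether a hospital contact makes an event serious, or whether planned surgery is an event at all. Here it goes further and withdraws AE status from the illness. For elective procedures that does little harm. For an unplanned emergency visit it means that the setting of care, not the event, decides whether the event enters a primary endpoint.

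AE and SAE status also drives oversight. The section 8.4 review unblinds the arms if any arm has an SAE or at least two AEs with a possible or stronger relation to study drug. Section 10.1 has the Data and Safety Monitoring Board (DSMB) review SAEs within 24 hours. Staff who follow the specific list and staff who follow the general recording rule would send different data to both.

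**Working it through.** The plan gives no figure on this point, so the check is a comparison of texts. Take one new event arising after the subject leaves the unit, and apply the section 8.1 list literally, then the general rule and the hospitalization default.

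| Course of the event | List read literally | General rule and default |
|---|---|---|
| Managed at home, reported by phone | AE (list does not apply) | AE |
| Emergency visit under 24 hours, no admission, judged not important | Not an AE | AE |
| Emergency visit, judged important medical or life-threatening | AE (exception) | AE |
| Admitted, not for the target disease, unplanned | SAE | SAE |
| Admitted for the target disease, not judged a worsening or rise in admissions | Neither AE nor SAE | SAE |
| Admitted for the target disease, judged a worsening or rise in admissions | SAE (exception) | SAE |

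The readings differ in rows 2 and 5. Row 2 is well defined and consists mainly of mild to moderate events. Row 5 has unknown reach, because the disease is not named.

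Row 2 is not remote. Sections 1.4.2.1 and 1.6 name falls in blood pressure as a risk. In the earlier healthy-subject studies, at higher doses for the most part, mean time to peak concentration was 3 to 6 hours and below-normal blood pressure took about 6 hours on average to recover. Observation in this trial is 6 hours (sections 3 and 6.2).

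**Illustration of the section 8.4 trigger.** The review has 5 subjects per arm. Let *p* be the chance that a subject has a related AE (at most one each) and *s* the share of such AEs not reported. Both are assumptions; the documents give neither. With *q* = *p*(1 − *s*), the chance of at least two is 1 − (1 − *q*)^5 − 5*q*(1 − *q*)^4.

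- *p* = 0.3, *s* = 0: *q* = 0.30; 1 − 0.168 − 0.360 = 0.472.
- *p* = 0.3, *s* = 0.25: *q* = 0.225; 1 − 0.280 − 0.406 = 0.315 after rounding.

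| *p* | *s* = 0 | 10% | 25% | 50% |
|---|---|---|---|---|
| 0.2 | 0.263 | 0.222 | 0.165 | 0.081 |
| 0.3 | 0.472 | 0.409 | 0.315 | 0.165 |
| 0.5 | 0.812 | 0.744 | 0.619 | 0.367 |

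This shows only that a two-event trigger in five subjects is sensitive to omissions. It does not estimate how many there would be.

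**The case against.** The strongest reply is that this is template wording, overridden in practice by the unqualified recording rule beside it, and that other safeguards exist. Staff must question subjects about AEs at every contact. The subject returns on Day 1 for orthostatic vital signs, examination and AE review (section 6.3). Vital sign changes are primary safety data in their own right (section 3.4). The DSMB sees unblinded data every other week during enrolment (section 8.5.1), and expected flu-like symptoms could reach the section 8.4 count without any emergency visit. One might add that the list speaks of reporting and the general rule of recording. These points limit the damage. They do not remove the conflict: no text ranks the two rules, and none says that an event not reported as an AE still enters the AE endpoint.

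Three stronger readings are tempting and are not supported.

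- *Sicker subjects drop out of the safety count.* Events are omitted, not subjects. Unplanned admissions outside the target-disease item stay in, as do important medical and life-threatening emergency visits.
- *Influenza and COVID-19 admissions disappear from view.* Reading the target disease as either is inference, and the worsening exception could cover a first admission in a healthy subject. COVID-19 hospitalization is an exploratory objective (section 2), COVID-19 evaluations are documented until resolution (section 3), and respiratory infections are a secondary endpoint compared across arms (sections 3.5 and 7.2). At most such admissions could be missing from the AE and SAE listing. Capture elsewhere does not confer AE or SAE status.
- *About two events per arm would be lost.* Section 1.4.2.1 reports IV fluids in 13 of 150 subjects (8.7%), and 25 × 0.087 = 2.2. But those doses ran from 2 to 50 µg, with only 6 + 6 = 12 of the 150 subjects at 10 µg or less; fluids were given inconsistently, at investigator discretion; and section 1.4.2.4 reports no treatment-related AEs at 1 µg. Fluid use is a far wider class than an emergency visit after discharge, without admission, judged not important. The section 8.4 review also has 5 per arm, where the same rate gives 5 × 0.087 = 0.43.

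**Conclusion.** The concern stands as a contradiction in the definition of a primary endpoint. Section 8.1, applied as written, leaves some new events out of the AE count depending on where care was given, while another sentence of that section and section 3.4 require them in. This is an error in the wording and not merely a missing detail, because a site following the list would be following the protocol. The certain part is the non-admitted emergency visit. The target-disease part is an undefined term whose reach cannot be settled from the text.

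No rate of omitted events can be derived from the documents, and no stated figure or planned analysis is shown to change. The trigger probabilities above rest wholly on assumed *p* and *s*. The conclusion rests on the literal text and on the absence of any statement about which rule prevails.

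**What to change.** In section 8.1:

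1. Reword the lead sentence so that the listed circumstances decide only whether the hospital contact or procedure by itself counts as an AE, or makes an event serious.
2. Add that any underlying condition that is new or has worsened is still recorded as an AE, wherever it was treated.
3. Delete the target-disease item. If it is kept, define the term so that admissions for influenza, COVID-19 or other respiratory infection are not exempt from the section's default that an AE causing hospitalization is an SAE.

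Carry the same wording into the guidance for the AE worksheet. The cost is a few sentences, with no added visits or procedures. Recorded AE and SAE counts may rise slightly.
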